10.6. Appendix 6: ECG Findings of Potential Clinical Concern

| ECG Findings That May Qualify as AEs |
|--|
| 
Marked sinus bradycardia (rate <40 bpm) lasting minutes.New PR interval prolongation >280 msec.New prolongation of QTcF to >480 msec (absolute) or by \geq60 msec from baseline.New-onset atrial flutter or fibrillation, with controlled ventricular response rate: ie, rate <120 bpm.New-onset type I second-degree (Wenckebach) AV block of >30 seconds' duration.Frequent PVCs, triplets, or short intervals (<30 seconds) of consecutive ventricular complexes. |
| ECG Findings That May Qualify as SAEs |
| 
QTcF prolongation >500 msec.New ST-T changes suggestive of myocardial ischemia.New-onset left bundle branch block (QRS >120 msec).New-onset right bundle branch block (QRS >120 msec).Symptomatic bradycardia.Asystole:
In awake, symptom-free participants in sinus rhythm, with documented periods of asystole \geq3.0 seconds or any escape rate <40 bpm, or with an escape rhythm that is below the AV node.In awake, symptom-free participants with atrial fibrillation and bradycardia with 1 or more pauses of at least 5 seconds or longer.Atrial flutter or fibrillation, with rapid ventricular response rate: rapid = rate >120 bpm.Sustained supraventricular tachycardia (rate >120 bpm) ("sustained" = short duration with relevant symptoms or lasting >1 minute). |

- Ventricular rhythms >30 seconds' duration, including idioventricular rhythm (heart rate <40 bpm), accelerated idioventricular rhythm (HR >40 bpm to <100 bpm), and monomorphic/polymorphic ventricular tachycardia (HR >100 bpm (such as torsades de pointes)).
- Type II second-degree (Mobitz II) AV block.
- Complete (third-degree) heart block.

ECG Findings That Qualify as SAEs

- Change in pattern suggestive of new myocardial infarction.
- Sustained ventricular tachyarrhythmias (>30 seconds' duration).
- Second- or third-degree AV block requiring pacemaker placement.
- Asystolic pauses requiring pacemaker placement.
- Atrial flutter or fibrillation with rapid ventricular response requiring cardioversion.
- Ventricular fibrillation/flutter.
- At the discretion of the investigator, any arrhythmia classified as an adverse experience.

The enumerated list of major events of potential clinical concern are recommended as “alerts” or notifications from the core ECG laboratory to the investigator and Pfizer study team, and not to be considered as all inclusive of what to be reported as AEs/SAEs.

10.7. Appendix 7: Abbreviations

The following is a list of abbreviations that may be used in the protocol.

| Abbreviation | Term |
|--------------------------|---|
| → | ongoing/continuous event |
| τ | tau |
| Abs | Absolute |
| ADA | anti-drug antibodies |
| AE | adverse event |
| ALC | Absolute lymphocyte count |
| ALT | alanine aminotransferase |
| ANC | absolute neutrophil count |
| AST | aspartate aminotransferase |
| AUC | area under the curve |
| AUC _τ | AUC from time 0 to time τ , the dosing interval |
| AUC _{14 days} | AUC from time 0 to Day 14 (336 hours) |
| AUC _{inf} | AUC from time 0 extrapolated to infinite time |
| AUC _{inf} (dn) | dose normalized AUC _{inf} |
| AUC _{last} | AUC from time 0 to T _{last} |
| AUC _{last} (dn) | dose normalized AUC _{last} |
| AV | atrioventricular |
| BMI | body mass index |
| BP | blood pressure |
| bpm | beats per minute |
| BUN | blood urea nitrogen |
| CD | Crohn's disease |
| CDE | Center of Drug Evaluation |
| CFR | Code of Federal Regulations |
| CIOMS | Council for International Organizations of Medical Sciences |
| CK | creatinine kinase |
| CKDEPI | Chronic Kidney Disease Epidemiology Collaboration |
| CL | clearance |
| CL/F | apparent clearance |
| C _{last} | last quantifiable concentration |
| C _{last*} | predicted serum concentration at the last quantifiable time point |
| C _{max} | maximum observed concentration |
| C _{max} (dn) | dose normalized C _{max} |
| CONSORT | Consolidated Standards of Reporting Trials |
| CRF | case report form |
| CRO | contract research organization |
| CRU | clinical research unit |
| CSR | clinical study report |
| CT | clinical trial |
| DCT | data collection tool |

| Abbreviation | Term |
|--------------|---|
| DILI | drug-induced liver injury |
| DMC | data monitoring committee |
| dn | dose normalized to 1 mg |
| DNA | deoxyribonucleic acid |
| DR3 | Death Receptor 3 |
| EC | ethics committee |
| ECG | electrocardiogram |
| eCRF | electronic case report form |
| EDP | exposure during pregnancy |
| EFD | embryo-fetal development |
| eGFR | estimated glomerular filtration rate |
| EMA | European Medicines Agency |
| eNCA | electronic non-compartmental analysis |
| ET | early termination |
| EU | European Union |
| EudraCT | European Clinical Trials Database |
| F | apparent bioavailability/estimate of bioavailability for the SC doses relative to IV dosing |
| FIH | first in human |
| FSH | follicle-stimulating hormone |
| GCP | Good Clinical Practice |
| GD | Gestation Days |
| GGT | gamma-glutamyl transferase |
| HBcAb | hepatitis B core antibody |
| HBsAb | hepatitis B surface antibody |
| HBsAg | hepatitis B surface antigen |
| HBV | hepatitis B |
| HBVDNA | hepatitis B DNA |
| HCVAb | hepatitis C antibody |
| HIPAA | Health Insurance Portability and Accountability Act |
| HIV | human immunodeficiency virus |
| HRT | hormone replacement therapy |
| IB | investigator's brochure |
| IBD | inflammatory bowel disease |
| ICD | informed consent document |
| ICH | International Council for Harmonisation |
| IFN | interferon |
| IgG | immunoglobulin G |
| IGRA | Interferon Gamma Release Assay |
| IL | interleukin |
| IND | investigational new drug application |
| INR | international normalized ratio |
| IP | investigational product |

| Abbreviation | Term |
|-----------------------|---|
| IRB | institutional review board |
| IUD | intrauterine device |
| IUS | Intrauterine hormone-releasing system |
| IV | intravenous |
| LBBB | left bundle branch block |
| LFT | liver function test |
| MAD | multiple ascending doses |
| MRI | magnetic resonance imaging |
| msec | millisecond |
| N/A | not applicable |
| NAb | neutralizing antibodies |
| NOAEL | no-observed-adverse-effect level |
| PC | positive control |
| PCRU | Pfizer Clinical Research Unit |
| PD | pharmacodynamic(s) |
| PK | pharmacokinetic(s) |
| PPD | purified protein derivative |
| PR | pulse rate |
| PT | prothrombin time |
| PVC | premature ventricular contraction/complex |
| QFT-G | QuantiFERON-TB GoldIn-Tube |
| Q2W | every 2 weeks |
| Q4W | every 4 weeks |
| QRS | part of electrocardiographic wave |
| QTc | corrected QT |
| QTcF | corrected QT (Fridericia method) |
| qual | qualitative |
| R _{ac} | observed accumulation ratio |
| R _{ac, Cmax} | observed accumulation ratio for Cmax |
| SAD | single ascending dose |
| SAE | serious adverse event |
| SAP | statistical analysis plan |
| SC | subcutaneous |
| SCr | serum creatinine |
| SoA | schedule of activities |
| SOP | standard operating procedure |
| SRSD | single reference safety document |
| sTL1A | soluble TL1A |
| SUSAR | suspected unexpected serious adverse reaction |
| TB | tuberculosis |
| Th1 | T helper type 1 |
| Th2 | T helper type 2 |
| Th9 | T helper type 9 |

| Abbreviation | Term |
|------------------|--------------------------------------|
| Th17 | T helper type 17 |
| TL1A | tumor necrosis factor like ligand 1A |
| T _{max} | time at which Cmax occurred |
| TNF | tumor necrosis factor |
| t _½ | terminal elimination half life |
| TBili | total bilirubin |
| UC | ulcerative colitis |
| ULN | upper limit of normal |
| US | United States |
| V _{ss} | volume of distribution |
| V _{z/F} | apparent volume of distribution |
| WBC | white blood cell |
| WOCBP | woman of childbearing potential |

1. VERSION HISTORY

Table 1. Summary of Changes

Version/ Date	Associated Protocol Amendment	Rationale	Specific Changes
1/ 08 Feb 2021	Original 29 Dec 2020	N/A	N/A
2/ 25 Apr 2022	Original 29 Dec 2020	To respond to the additional comments	
 • Section 3.4: changed the wording for the baseline to be more precise. • Section 3.5.1: changed the wording for the definition of TEAE to be consistent with the algorithm of TEAE defined in the newest version of CaPS. • Sections 3.5.2, 3.5.3: removed the hours of collection days to be flexible in the analyses. • Section 3.5.5: removed the hours of collection days to be flexible in the analyses, and added “The full list of ...” in the end of second paragraph for clarification. • Section 4: added content and modified the format of table to be consistent with the newest SAP template. • Section 5.2: removed “or summaries”. • Section 6.1.2: added injection site reactions to the endpoint of AEs. • Section 6.2.1: removed “AUC_{14days}(dn)” and added content for completeness of section. • Section 6.3: removed this section and re-number the subsequent sections. • Section 6.4.1: added more demographic examples. • Section 6.4.2: removed “for safety”. • Section 6.5: added COVID-19 related safety analyses • Section 9, Appendix 1: added and removed abbreviations to adjust to the content of SAP.

2. INTRODUCTION

PF-06480605 is a fully human IgG1 monoclonal antibody against Tumor Necrosis Factor like Ligand 1A (TL1A), a member of the tumor necrosis factor (TNF) family of cytokines, that is currently in development for the treatment of Crohn's disease (CD) and ulcerative colitis (UC). The mechanism of action of PF-06480605 is to neutralize the binding and subsequent signaling of TL1A to its functional receptor Death Receptor 3 (DR3) on immune cells of the innate and adaptive immune system.

The purpose of the study is to evaluate the PK, safety, tolerability, immunogenicity, and PD of PF-06480605 in Chinese healthy adult participants. The information of the PK, safety, tolerability, immunogenicity, and PD in Chinese healthy participants is being collected to support further clinical development as well as drug registration in China.

This statistical analysis plan (SAP) provides the detailed methodology for summary and statistical analyses of the data collected in Study B7541013. This document may modify the plans outlined in the protocol; however, any major modifications of the primary endpoint definition or its analysis will also be reflected in a protocol amendment.

2.1. Study Objectives, Endpoints, and Estimands

Estimands are not applicable to this Phase 1 study.

Objectives	Endpoints
Primary:	Primary:

 To characterize the PK of PF-06480605 following administration of single SC dose of PF-06480605 450 mg and 150 mg (if needed) in Chinese healthy adult participants. To evaluate the safety and tolerability following administration of single SC dose of PF-06480605 450 and 150 mg (if needed) in Chinese healthy adult participants. 	
 Serum PF-06480605 primary PK parameters, as permitted by data: C_{max}, T_{max}, $AUC_{14\text{ days}}$, AUC_{inf}, and $t_{1/2}$. Assessment of AEs, vital signs, 12-lead electrocardiograms, physical examination findings and clinical safety laboratory measurements.
Secondary:	Secondary:

 To further evaluate the PK of PF-06480605. To evaluate the immunogenicity of PF-06480605. To evaluate the PD biomarker (if feasible) which may be informative in demonstrating the pharmacologic effect of PF-06480605. 	
 Serum PF-06480605 PK parameters, as permitted by data: AUC_{last}, $C_{max(dn)}$, $AUC_{inf(dn)}$, and $AUC_{last(dn)}$, V_z/F and CL/F. Incidence of the development of ADA and NAb. Total sTL1A protein concentration in serum.

2.2. Study Design

This is a Phase 1, single-center, randomized, double-blind, third-party open (participant blind, investigator blind, sponsor open), placebo -controlled study to investigate PK, safety, tolerability, immunogenicity, and PD of PF-06480605 following a single subcutaneous dose of PF-06480605 450 mg and 150 mg (if needed) in Chinese healthy adult participants. Optional 150 mg cohort will be conducted only if data from 450 mg cohort does not confirm expected PK based on previous studies in healthy Western and Japanese participants as well as UC patients.

A maximum of approximately 24 participants (18 with active treatment and 6 with placebo) will be randomized and receive the investigational product such that approximately 12 participants are assigned to each cohort (450 mg and 150 mg) to ensure that 11 evaluable participants per cohort will complete the study. Participants will be enrolled to both cohorts sequentially, starting with the 450 mg cohort first. When the 150 mg cohort is determined to be needed, the 150 mg cohort with entirely new participants will be opened.

The 150 mg cohort will be started only if it indicates the ethnic PK difference (eg, more than two-fold higher exposure) based on all available serum concentrations data of PF-06480605 obtained until the timing when the PK sample is collected at Day 14 after administration, by comparing the dose-normalized mean exposures (or dose-normalized mean concentrations profiles) in this study versus dose-normalized mean exposures in Western study B7541001 and Japanese study B7541006.

Table 2. Randomization Scheme

Cohort	Treatment	Number of participants
1	PF-06480605 450 mg	9
	Placebo	3
2 (optional)	PF-06480605 150 mg	9
	Placebo	3

Participants, who drop out from the study if the number of participants completing at least the follow-up visit at Day 57 per cohort decreases to 10 or lower, will be replaced.

If a participant discontinues before completing the part of the study to which they have been randomized, or withdraws for reasons unrelated to the safety of the investigational product, the participant may be replaced at the discretion of the investigator upon consultation with the sponsor.

Within 28 days of successful completion of the screening process, eligible participants will be enrolled and randomized to receive a single dose of PF-06480605 450 mg or 150 mg (if needed) or placebo. Participants will be admitted into the CRU approximately 1 day prior to dosing and required to stay overnight in the CRU at least through completion of the Day 5 evaluations. Participants will return for outpatient follow-up visits through Day 114.

3. ENDPOINTS AND BASELINE VARIABLES: DEFINITIONS AND CONVENTIONS

3.1. Primary Endpoint(s)

The primary endpoints consist of PK and safety endpoints.

- Serum PF-06480605 primary PK parameters, as permitted by data: C_{max} , T_{max} , $AUC_{14\text{ days}}$, AUC_{inf} , and $t_{1/2}$.
- Assessment of AEs, vital signs, 12 lead electrocardiograms, physical examination findings and clinical safety laboratory measurements.

3.2. Secondary Endpoint(s)

The secondary endpoints are additional PK, immunogenicity and PD biomarker endpoints defined as follows.

- Serum PF-06480605 PK parameters, as permitted by data: AUC_{last} , $C_{max}(\text{dn})$, $AUC_{inf}(\text{dn})$, and $AUC_{last}(\text{dn})$, V_z/F and CL/F .
- Incidence of the development of ADA and Nab.
- Total sTIL1A protein concentration in serum.

3.3. Other Endpoint(s)

There are no other endpoints defined in this study.

3.4. Baseline Variables

Baseline value is defined as the latest value before receiving the dose of study intervention.

3.5. Safety Endpoints

3.5.1. Adverse Events

An adverse event is considered treatment emergent if the event starts during the effective study period (CRU confinement and follow-up visits).

All events that start on or after the dosing day and time, if collected, but before the end of study will be flagged as TEAEs. The algorithm will not consider any events that started prior to the dose date. If an AE starts on the same day as the dose date, it will be considered treatment emergent unless the CRF data indicates otherwise via explicitly recording time for AE onset and treatment dosing.

3.5.2. Vital Signs

Supine BP, PR measurements and axillary temperature are collected during the CRU confinement on Day 1 and Day 5, and during the follow-up visits on Day 10 and Day 114/ET.

3.5.3. Electrocardiograms

Single 12-Lead ECGs are collected during the CRU confinement on Day 1 and Day 5, and during the follow-up visits on Day 10 and Day 114/ET. Repeat ECGs may be taken following the study protocol at each assessment time.

Changes from baseline for the ECG parameters: QT interval, heart rate, QTc interval, PR interval, and QRS complex will be summarized by treatment and time.

3.5.4. Physical Examination

Height and body weight are only collected at screening. A full physical examination may be done at screening or Day -1. Brief physical examination to follow up open AEs after Day -1 may be done.

3.5.5. Laboratory Data

The safety laboratory tests of hematology, chemistry and urinalysis are performed during the screening, the CRU confinement on days: -1, 2 and 5, and the follow-up visits on days: 10, 15, 57, 85 and 114/ET.

Additional laboratory results may be reported on these samples as a result of the method of analysis or the type of analyzer used by the clinical laboratory, or as derived from calculated values. These additional tests would not require additional collection of blood. The full list of laboratory tests/assessments is shown in Table 4 in the protocol.

Hematology	Chemistry	Urinalysis
Hemoglobin	BUN and creatinine	pH
Hematocrit	Glucose (fasting)	Glucose (qual)
RBC count	Calcium	Protein (qual)
MCV	Sodium	Blood (qual)
MCH	Potassium	Ketones
MCHC	Chloride	Nitrites
Platelet count	Total CO ₂ (bicarbonate)	Leukocyte esterase
WBC count	AST, ALT	Urobilinogen
Total neutrophils (Abs)	Total bilirubin	Urine bilirubin
Eosinophils (Abs)	Alkaline phosphatase	Microscopy ^a
Monocytes (Abs)	Uric acid	
Basophils (Abs)	Albumin	
Lymphocytes (Abs)	Total protein	
	Additional Tests (Needed for Hy's Law)	
	AST, ALT (repeat) Total bilirubin (repeat) Albumin (repeat) Alkaline phosphatase (repeat) Direct bilirubin Indirect bilirubin Creatine kinase GGT PT/INR	

a. Only if urine dipstick is positive for blood, or leukocyte esterase.

To determine if there are any abnormalities of potential clinical concern, the hematology, chemistry and urinalysis safety tests will be assessed against the criteria specified in the CDISC and Pfizer standards (CaPS). The assessment will take into account whether each participant's baseline test result is within or outside the laboratory reference range for the particular laboratory parameter.

4. ANALYSIS SETS (POPULATIONS FOR ANALYSIS)

Data for all participants will be assessed to determine if participants meet the criteria for inclusion in each analysis set prior to unblinding and releasing the database and classifications will be documented per standard operating procedures.

For purposes of PK/PD, safety and immunogenicity analyses, the following analysis sets are defined:

Population	Description	Applicable Analysis (for additional information refer to section 6)
Safety	All randomized participants who applied at least 1 dose of study intervention.	Analysis for safety endpoints
PK Concentration	All randomized participants who applied at least 1 dose of study intervention and for whom at least 1 concentration value is reported.	Analysis for PK concentration
PK Parameter	All randomized participants who applied at least 1 dose of study intervention and for whom at least 1 of the PK parameters of interest (e.g., AUC_{inf} and C_{max}) is calculated.	Analysis for PK parameters
Immunogenicity	All randomized participants who applied at least 1 dose of study intervention with at least 1 post-treatment anti-drug (PF-06480605) antibody determination.	Analysis for immunogenicity endpoints
PD	All randomized participants who have at least 1 PD assessment.	Analysis for PD biomarkers

All analyses will not include data from participants who are randomized but not treated. If a participant receives a treatment that is not consistent with the treatment they were randomly assigned to, then the participant will be reported under the treatment that the participant actually received for all PK/PD, safety and immunogenicity analyses, where applicable.

5. GENERAL METHODOLOGY AND CONVENTIONS

5.1. Hypotheses and Decision Rules

No formal statistical hypothesis testing will be conducted the analyses in this study.

5.2. General Methods

No formal statistical tests will be performed. Descriptive analyses will be provided for all endpoints by treatment for each cohort.

Additionally, a population PK model will be developed to characterize the PK and assess the effect of ethnicity on PK using all available data. The detailed analysis plans will be described in a separate pharmacometric analysis plan.

5.2.1. Analyses for Binary Endpoints

Number and percentage of participants in each category will be used to summarize the endpoints, if not otherwise specified.

5.2.2. Analyses for Continuous Endpoints

The summary statistics n, arithmetic mean, median, standard deviation (SD), minimum and maximum will be used to summarize the endpoints, if not otherwise specified.

The summary statistics for PK parameters are described in Section 6.2.

5.2.3. Analyses for Categorical Endpoints

Number and percentage of participants in each category will be used to summarize the endpoints, if not otherwise specified.

5.3. Methods to Manage Missing Data

Missing data will not be imputed.

5.3.1. Concentrations Below the Limit of Quantification

In all data presentations (except listings), PK and PD concentrations below the limit of quantification (BLQ) will be set to zero. In listings, BLQ values will be reported as “<LLQ”, where LLQ will be replaced with the value for the lower limit of quantification.

5.3.2. Deviations, Missing Concentrations and Anomalous Values

In summary tables, plots of mean profiles and plots of median profiles, summary statistics will be calculated by setting concentrations to missing if one of the following cases is true:

- A concentration has been collected as ND (Not Done) or NS (No Sample).
- A deviation in sampling time is of sufficient concern or a concentration has been flagged anomalous by the pharmacokineticist.

Note that summary statistics will not be presented at a particular time point if more than 50% of the data are missing.

5.3.3. PK Parameters

Actual PK sampling times will be used in the derivation of PK parameters.

If a PK parameter cannot be derived from a participant's concentration data, the parameter will be coded as NC (Not Calculated). Note that NC values will not be generated beyond the day a participant discontinues.

In summary tables, summary statistics will be calculated by setting NC values to missing; and summary statistics will not be presented at a particular time point if more than 50% of the data are missing.

If an individual participant has a known biased estimate of a PK parameter (eg, due to known loss of drug during SC administration), this will be footnoted in summary tables and will not be included in the calculation of summary statistics.

6. ANALYSES AND SUMMARIES

6.1. Primary Endpoint(s)

The primary endpoints include PK and safety endpoints.

The primary PK parameters will be calculated from the concentration-time values for each participant, as applicable, using noncompartmental analysis as described in the protocol. The primary PK parameters will be listed and summarized for participants in the PK parameter analysis set. Each PK parameter will be summarized by dose (450 mg, 150 mg [if needed]) and will include the set of summary statistics as specified in the table in Section 6.1.1.

The safety endpoints will be listed and summarized by treatment (450 mg, 150 mg [if needed] and placebo) for participants in the safety analysis set. All participants received placebo in either 450 mg or 150 mg (if needed) cohort will have a pooled placebo group.

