Considering these results from Study B7541001, exposure following a single 450 mg SC dose is much less likely to exceed the exposure of the single 800 mg IV dose observed in Study B7541001 and is expected to be safe and tolerable. As expected, the preliminary data in Japanese Study B7541006 demonstrated that single dose up to 450 mg SC was clinically safe and well tolerated in Japanese healthy participants, and no AE was observed in 450 mg cohort. Therefore, the concern of unacceptable safety and tolerability is not expected in Chinese healthy participants with administration of a single 450 mg SC dose.

The preliminarily partial PK data in Japanese Study B7541006 showed no ethnic PK difference between Japanese and Westerners by comparing the individual concentration-time profiles till Day 5 (around C_{max}). The full PK profile in Japanese healthy participants will be available in Feb/Mar 2021, and the comparison with Western healthy participants will be performed afterwards.

Taken together, the likelihood of needing 150 mg cohort is low. 150 mg cohort will be conducted only if any of the following scenarios is observed in Chinese healthy participants following a single 450 mg SC dose:

- It indicates the ethnic PK difference (eg, more than two-fold higher exposure) based on all available serum concentrations data of PF-06480605 obtained until the timing the PK sample at day 14 after administration, by comparing the dose-normalized mean exposures (or dose-normalized mean concentrations profiles) in this study versus dose-normalized mean exposures in study B7541001 and B7541006, and/or,
- Sponsor need to initiate 150 mg cohort for other consideration.

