6.1.1. Administration

Participants will receive study intervention at approximately 0800 hours (plus or minus 2 hours). Study medication does not require fasting, but it should be noted that the safety laboratory test at Day -1 prior to the study medication need a fast of at least 4 hours. Study medication will be administered subcutaneously. Injection should occur at a site on the abdomen. All participants will be administered one or more 1.5 mL SC injections. The number of SC injections depends on the doses such that one SC injection for 150 mg, and three SC injections for 450 mg. Thus, the number of SC injections will be maximal 3 times. Each injection is to occur at a different site on the abdomen, approximately 1 cm apart.

Administer study intervention according to the IP manual.

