6.3.2. Breaking the Blind

The method for breaking the blind in this study will be manual. A sealed envelope that contains the study intervention assignment(s) for each participant will be provided to the investigator. The sealed envelope will be retained by the investigator (or representative) in a secured area. In case of an emergency, the investigator has the sole responsibility for determining if unblinding of a participant's treatment assignment is warranted. Participant safety must always be the first consideration in making such a determination. If the investigator decides that unblinding is warranted, the investigator should make every effort to contact the sponsor prior to unblinding a participant's treatment assignment unless this could delay further management of the participant. If a participant's treatment assignment is unblinded, the sponsor must be notified within 24 hours after breaking the blind. When the blinding code is broken, the reason must be fully documented and entered on the CRF/DCT.

Once the study is complete, all envelopes (sealed and opened) must be inventoried and retained until authorization for destruction has been provided.

Blinding codes should be broken only in exceptional circumstances when knowledge of the actual treatment code is absolutely essential for further management of the participant. Investigators are encouraged to discuss with a member of the study team if they believe that unblinding is necessary. When the blinding code is broken, the reason must be fully documented and entered on the CRF/DCT.

This is an investigator- and participant-blind (Sponsor open) placebo-controlled study. Blood specimens will be obtained from all participants for PK analysis to maintain the study blind at the investigator site. The investigator site staff with the exception of the site pharmacist(s), pharmacy assistant(s) and study drug administrator(s) and blinded study monitor, if assigned, will be blinded to study treatment. Other Pfizer personnel will be unblinded to participant treatments in order to permit real-time interpretation of the safety and PK data; and provide

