8.2.7. Injection Site Reactions

Each participant will be monitored a minimum of 2 hours after the study intervention. After 2 hours the injection site will be monitored for redness, swelling, or any type of inflammation and this should be recorded as an injection site reaction, if applicable on the appropriate CRF. If the participant has a delayed reaction, (after they leave the investigative site) this should also be captured as an injection site reaction, on the adverse event CRF page.

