6.1.2. Adverse Events

AEs (including injection site reactions) will be listed and summarized following CaPS.

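### Does pooling placebo across the two cohorts spoil the injection site reaction summary if the 150 mg cohort is run?

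*SAP*

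**What the plan says.** SAP 6.1 sets the columns for all safety endpoints: 450 mg, 150 mg if that cohort is run, and placebo. It then adds: "All participants received placebo in either 450 mg or 150 mg (if needed) cohort will have a pooled placebo group". SAP 6.1.2 brings injection site reactions under this rule: "AEs (including injection site reactions) will be listed and summarized following CaPS". SAP 5.2, headed General Methods, is broader: "Descriptive analyses will be provided for all endpoints by treatment for each cohort". Protocol 9.4.2 has similar by-cohort wording for safety data, qualified by a phrase limiting it to where that is appropriate.

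Protocol 6.1.1 says that every participant receives one or more 1.5 mL injections, and that the number follows the dose: "one SC injection for 150 mg, and three SC injections for 450 mg". It gives no separate count for placebo. Protocol 6.3.2 states: "This is an investigator- and participant-blind (Sponsor open) placebo-controlled study". Protocol 8.2.7 describes the local assessment: "After 2 hours the injection site will be monitored for redness, swelling, or any type of inflammation". On whether the second cohort will be needed at all, Protocol 4.3 concludes that "the likelihood of needing 150 mg cohort is low".

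**The concern.** Most adverse events have no obvious link to how many needles a participant receives. Injection site reactions do: three injections give three chances of a reaction. If placebo participants get the same number of injections as the active participants in their cohort, which the participant blind all but requires, a pooled placebo group mixes two levels of exposure to the procedure.

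The resulting error would have a known direction. With no drug effect at all, 450 mg would tend to look worse than pooled placebo and 150 mg better, which resembles a dose trend. Safety and tolerability is a primary objective, so a misleading tolerability table would matter.

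There is also a question of wording. SAP 5.2 speaks of all endpoints by treatment for each cohort, SAP 6.1 pools placebo, and neither section refers to the other.

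**Working it through.** **Plan figures, reproduced.** Vial strength is 100 mg/mL (Protocol 6.1) and each injection is 1.5 mL (Protocol 6.1.1).

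- 450 mg: 450 / 100 = 4.5 mL; 4.5 / 1.5 = 3 injections.
- 150 mg: 150 / 100 = 1.5 mL; 1.5 / 1.5 = 1 injection.
- 12 per cohort at 3:1 (Protocol 9.2): 9 active and 3 placebo; over two cohorts, 18 and 6.

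These agree with the documents.

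**Pooled column, if both cohorts run and placebo matches its cohort.** Three people have 3 injections and three have 1, so the mean is (3×3 + 3×1) / 6 = 2.0 per person, against 3 and 1 in the active arms.

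**Size of the shift.** The documents give no reaction rate per injection, so p is assumed to be 5, 10 or 20%, with independent injections and no drug effect. Expected participant rates are q3 = 1 − (1 − p)³ with three injections and q1 = p with one. The pooled rate is (q3 + q1) / 2, so the shift is (q3 − q1) / 2: too low as a control for 450 mg and too high for 150 mg by the same amount.

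| p | q3 | q1 | pooled | shift (points) | shift, within-person correlation 0.5 |
|---|---|---|---|---|---|
| 5% | 14.3% | 5% | 9.6% | 4.6 | 2.0 |
| 10% | 27.1% | 10% | 18.55% | 8.55 | 3.7 |
| 20% | 48.8% | 20% | 34.4% | 14.4 | 6.4 |

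The last column uses a beta-binomial model. With full within-person correlation the shift is zero. One participant in a column of six is 1/6 = 16.7 points, so every shift in the table is smaller than one participant.

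**Would splitting placebo give a better control?** Compare the standard error of a three-person rate, √(q(1 − q)/3), with the root mean squared error of the six-person pooled rate, √{[3·q3(1 − q3) + 3·q1(1 − q1)]/36 + shift²}.

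At p = 10%:

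- 450 mg control, split: √(0.271 × 0.729 / 3) = 25.7 points.
- 150 mg control, split: √(0.10 × 0.90 / 3) = 17.3 points.
- Pooled: √(0.1548² + 0.0855²) = 17.7 points.

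| p | 450 mg: split vs pooled | 150 mg: split vs pooled |
|---|---|---|
| 5% | 20.2 vs 12.8 | 12.6 vs 12.8 |
| 10% | 25.7 vs 17.7 | 17.3 vs 17.7 |
| 20% | 28.9 vs 23.4 | 23.1 vs 23.4 |

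Even with its bias counted against it, the pooled column has clearly smaller error for 450 mg and practically the same error for 150 mg. A three-person column moves in steps of 1/3 = 33 points, too coarse to show shifts of 2 to 14 points.

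**The two column rules.** SAP 5.2 states a general convention. SAP 6.1 names the safety columns and says outright that placebo is pooled. A programmer building the safety tables has one specific instruction to follow, and the SAP is allowed to modify the protocol's outline (Protocol 9; SAP 2).

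**The case for a change.** The best case for a change is that it would cost very little. The SAP provides for the 150 mg cohort throughout, so that branch ought to be fully specified. Version 2 of the SAP added injection site reactions to the adverse event section and thereby placed them under the pooling rule without an exception. The bias has a predictable direction, and placebo by cohort is the only information within the study on what extra injections do without drug. One could keep the pooled column and add two cohort columns beside it, so the precision argument against replacing it would not apply.

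Part of this stands. If both cohorts run, the pooled column very probably does mix injection counts, and SAP 5.2 does not mention the exception in 6.1. A footnote giving placebo injection site reactions by cohort would help a reader.

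What does not follow is that the plan must change. SAP 6.1 and 6.1.2 already call for listings as well as summaries. With at most six placebo participants, and cohorts enrolled one after the other with entirely new participants, each placebo reaction can be traced to its cohort, provided the listing carries participant or cohort identifiers; that layout follows the sponsor's standards, which are not in the documents. Nor does the SAP specify an active-minus-placebo estimate or test that the shift could bias; the comparison is an informal reading across columns.

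The higher assumed rates also fit poorly with the nearest evidence. Protocol 4.3 reports no adverse event in the 450 mg cohort of the Japanese study, which had 8 participants (Protocol 2.2.2.1.3). With three independent injections each, the chance of no reaction in 8 people is (1 − p)²⁴: 0.29 at 5%, 0.08 at 10% and 0.005 at 20%. Those data are preliminary, that study's injection count is not given, and its adverse event statement is taken to cover injection site reactions, so this is only a pointer towards the smaller shifts.

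**Conclusion.** No change to the plan follows. Pooling placebo for safety is a stated choice and a fair trade-off with three placebo participants per cohort.

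The effect is zero if only the 450 mg cohort runs. If both run, the shift is 4.6 to 14.4 points under independent injections at assumed rates of 5 to 20%, 2.0 to 6.4 points at within-person correlation 0.5, and nil at full correlation. All of these are below the 16.7 points that one participant represents in the pooled column. They rest on the assumed rates, on no drug effect, and on placebo matching its cohort's injection count, which is inferred from the blind. By-cohort placebo columns would be an extra display that alters no planned result or conclusion.

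The difference between SAP 5.2 and 6.1 is a general rule followed by an explicit, more specific one. Saying so in 5.2 would be an editorial courtesy; analysts will produce the intended tables without it.
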